9.2 Sample Size and Randomization

9.2.1 Treatment Assignment Procedures

Three Tele-Savvy programs, with 10 caregivers in each Tele-Savvy program cohort, will be held sequentially at each health care system site, for a total of 60 caregivers in 6 Tele-Savvy cohorts. Recruitment will occur in three waves, whereby caregivers will be randomly assigned at a 3:2 ratio to either Tele-Savvy or the attention control group until the first Tele-Savvy cohort is filled (first wave), followed by the same randomization procedure until the second and third Tele-Savvy cohorts are filled.

9.3 Interim analyses and Stopping Rules

No interim analyses are planned.

9.4 Outcomes

9.4.1 Primary outcome

The primary outcome will be *caregiver mastery* of skills required to adequately fulfill the roles of being a dementia family caregiver. This primary outcome is consistent with the Social Learning theory^{42,43} underlying the Tele-Savvy intervention and with the content and learning dynamics of Tele Savvy sessions. Caregiver mastery will be measured using the mastery items from the measure developed by Pearlin and colleagues⁵³; this measure was used as the primary outcome in the Tele-Savvy efficacy study.⁴⁷ This outcome will be measured at study baseline for each caregiver (pre-randomization), 3 months post-randomization for all caregivers, and 6 months post-randomization for caregivers in the first and second waves.

9.4.2 Secondary outcomes

Secondary outcomes, also used in the Tele-Savvy efficacy study, will include *caregiver reactions* to behavioral and psychological symptoms expressed by persons living with dementia, using the Revised Memory and Behavior Problem Checklist, caregiver reactions scale,⁵⁴ and *perceived stress* using the global measure of perceived stress measure.⁵⁵

9.5 Data Analyses

The proposed sample size is for 60 caregivers randomized to a Tele-Savvy group and 40 caregivers randomized to an attention control group with data collection at 2 primary time points (baseline and 3 months (post treatment)). This design is adequately powered at 80% power and 5% level of significance to detect medium effect sizes for the group effect (Cohen's $f=0.285$), within subject time effect ($f=0.282$) and group-by-time treatment effect ($f=0.282$) using repeated measures analysis of variance (RM-ANOVA).^{57,58} This expected effect size is supported by previously measured improvements in caregiver mastery from the "Testing Tele-Savvy" study, NIH R01AG054079. We also intend to collect an additional follow-up time point at 6 months as a measure of sustainability of the treatment for approximately 2/3 of the participants (40 in Tele-

Savvy and 26 in attention control). For this smaller sample with a third time point we will be able to detect larger effects sizes ($f=0.350$ for group, $f=0.388$ for the time and group-by-time effects). In the “Testing Tele-Savvy” study, an effect size of $f=0.46$ was recorded for caregiver mastery improvements in active Tele-Savvy program participants. All data will be reviewed for completeness prior to analysis. All survey instruments will be scored and reliability computed prior to analysis. All measures will be assessed for normality and modeling assumptions with mathematical transformation applied as necessary prior to analysis. Multilevel mixed linear models (MLM) will be performed to utilize all data collected at each time point for all caregivers to assess changes in measures over time adjusting for attrition as needed. MLM will also adjust for the non-independence of the data collected across time nested within each subject. Post hoc pairwise comparisons between time points within subjects will be performed using Sidak error rate adjustments to control for multiple comparisons error rate inflation. Cohort number and clinical site will also be evaluated to see if any additional clustering effects are noted within each cohort or at each clinical site. Additionally, after performing an intent-to-treat (ITT) analysis, a follow-up analysis will also be conducted to see what if any additional effects were seen for subjects who were adherent versus those who weren’t, looking at the number of sessions attended for potential dose effect. The demographics of the subjects will also be evaluated as potential covariates for the statistical models. All statistical tests will be performed at 5% level of significance, with 95% confidence intervals reported for all effect sizes.

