consent for research purposes under the Revised Common Rule. We provide justifications for the request in section 6.2.

Recruitment will proceed in 3 waves at each site, with caregivers in each wave randomly assigned either to a Tele-Savvy program or an attention control program called Caregiving During Crisis. The recruitment goal at each site in each wave is to enroll 10 caregivers for a Tele-Savvy program cohort and 6-7 caregivers to receive the Caregiving During Crisis self-guided program.

The study biostatistician will be responsible for generating randomization strings for each study site during each wave of recruitment, and for making the randomization strings available electronically in a secure location for access by the study coordinator.

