The administrative study coordinator will electronically access the appropriate study site's randomization string (strings will be generated by the study biostatistician, see Section 4.3) after a caregiver returns completed baseline assessment forms. Randomization results will reveal whether the caregiver is assigned to the Tele-Savvy program or to the attention control group. Randomization will be performed within business 3 days of receipt of completed baseline assessment forms. The administrative study coordinator will then notify the Tele-Savvy facilitator at each study site of the randomization result, and the facilitator will notify caregivers about the treatment group to which they are assigned. The statistician will provide the randomization scheme (random sorting using 10% maximum allowable deviation using PASS 2020 software⁵⁶), which will be applied after the baseline assessment. For the Tele-Savvy intervention, because 10 caregivers at each site must be assembled in order to convene a cohort, a window of up to 3 weeks will be allowed between randomization of a caregiver to that treatment group and initiation of the intervention. For the attention control group, caregivers will be permitted to access the Caregiving During Crisis program anytime beginning 3 days after randomization.

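### Section 9.5 states and powers the 3-month mastery effect only as a change from baseline and leaves baseline handling unstated; one sentence fixing a common baseline mean (or a baseline covariate) would add precision at no cost

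*Combined protocol and SAP*

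**What the plan says.** The hypothesis in section 9.1 is greater improvement in mastery from baseline to 3 months with Tele-Savvy than with the control program. Section 9.5 sizes the study for 60 and 40 caregivers "with data collection at 2 primary time points (baseline and 3 months (post treatment", at 80% power and the 5% level, for a "group-by-time treatment effect ($f=0.282$) using repeated measures analysis of variance". The analysis model follows in the same section: "Multilevel mixed linear models (MLM) will be performed to utilize all data collected at each time point for all caregivers to assess changes". Demographics are the only covariates mentioned, and only as candidates. On site and cohort the text is: "Cohort number and clinical site will also be evaluated to see if any additional clustering effects are noted".

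Three other sections matter here. On mastery, section 9.4.1 says: "This outcome will be measured at study baseline for each caregiver (pre-randomization), 3 months post-randomization for all caregivers". Under section 6.2.2 the randomization string is opened only "after a caregiver returns completed baseline assessment forms". Section 4.3 makes the biostatistician responsible for "generating randomization strings for each study site during each wave of recruitment".

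**The concern.** The outcome, the time point and the between-arm comparison are all clear. What is open is how baseline mastery enters the model. The only form of the treatment effect that the plan states and powers is a difference in change. That form subtracts the whole baseline value, whatever its correlation with the 3-month value, and so carries baseline noise into the estimate. Conditioning on baseline, or using the fact that randomization makes the arms' expected baseline means equal, removes that noise.

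The total is fixed at 100, section 8 rules out replacing caregivers who discontinue, and section 9.5 promises 95% confidence intervals for all effect sizes. Interval width is therefore worth improving when it costs nothing.

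Site and wave are a smaller matter. They define the randomization strings, yet their place in the model is left to evaluation.

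**Working it through.** **The plan's own figure.** Inputs from section 9.5: N=100 (60 and 40), two time points, f=0.282, 5% level. The noncentrality is λ = N·f² = 100 × 0.282² = 7.952. With 1 and 98 degrees of freedom, power is 79.7%, so the stated 80% reproduces. With two time points this is the two-sample test on change scores, with a difference of 0.282/√(0.6×0.4) = 0.576 SDs of change. No baseline adjustment is built in.

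**Variance with and without adjustment.** Let ρ be the correlation of mastery at baseline and 3 months (assumed; not in the documents), with equal SD of 1 at both times.
- Change score: 2(1−ρ).
- Common baseline mean or baseline covariate: 1−ρ².
- Ratio: k = (1+ρ)/2.

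If the 3-month SD is s times the baseline SD, the change-score variance exceeds the adjusted one by (1+s²−2ρs) − s²(1−ρ²) = (1−ρs)². This is never negative, so adjustment does not lose precision beyond one degree of freedom.

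**No attrition, independent caregivers.** The interval shrinks by 1−√k. Adjusted power uses λ = 7.952/k with 94 denominator degrees of freedom (100, less 2 for arms, 1 for baseline, 3 for site and wave).

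| ρ | k | λ | Interval narrower by | Power: change to adjusted |
|---|---|---|---|---|
| 0.3 | 0.65 | 12.23 | 19% | 80% to 93% |
| 0.5 | 0.75 | 10.60 | 13% | 80% to 90% |
| 0.7 | 0.85 | 9.36 | 8% | 80% to 86% |
| 0.8 | 0.90 | 8.84 | 5% | 80% to 84% |
| 0.9 | 0.95 | 8.37 | 3% | 80% to 82% |

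Site (1 df) and wave (2 df) take the denominator from 97 to 94, which costs less than 0.1 point of power.

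**Attrition.** No rate is given, so 10% and 20% are assumed, equal in both arms and ignorable. The planned model uses all data, so dropouts' baselines count even without a baseline constraint. For a fraction a lost, the planned contrast has relative variance (1−ρ²)/(1−a) + (1−ρ)², and the adjusted one (1−ρ²)/(1−a). Example at a=0.2, ρ=0.5: planned 0.75/0.8 + 0.25 = 1.1875, λ = 7.952 × 1/1.1875 = 6.70, power 72%; adjusted 0.75/0.8 = 0.9375, λ = 7.952/0.9375 = 8.48, power 82%.

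| ρ | 10% lost: planned to adjusted | 20% lost: planned to adjusted |
|---|---|---|
| 0.3 | 77% to 91% | 73% to 87% |
| 0.5 | 76% to 86% | 72% to 82% |
| 0.7 | 76% to 82% | 72% to 77% |
| 0.8 | 76% to 80% | 71% to 75% |
| 0.9 | 76% to 77% | 71% to 72% |

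**Clustering in Tele-Savvy groups.** Section 9.2.1: "Three Tele-Savvy programs, with 10 caregivers in each Tele-Savvy program cohort, will be held sequentially at each health care system site". Only that arm is grouped. An intraclass correlation (ICC, assumed) multiplies the variance of the arm difference by [(1+9·ICC)/60 + 1/40]/(1/60 + 1/40) = 1 + 3.6·ICC, which is 1.18 at ICC 0.05. Take the ICC as the between-group share of baseline-adjusted 3-month variance, arising after baseline. With clustering modelled in both analyses, the interval ratio is √[k(1+3.6·ICC)/(1+3.6·ICC·k)]. At ICC 0.05 the interval narrows by 17, 12, 7, 4 and 2% over the same ρ values. In simulation with a group term in both models (ρ=0.5, ICC 0.05, no attrition, 4,000 trials), power was 62.5% for change and 73.9% adjusted.

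**The case against.** **Silence is not a commitment.** A reader might infer that the plan commits to an unadjusted change-score analysis. The documents do not support that. The description of the mixed model lists no fixed effects, so a common baseline mean is neither stated nor excluded. What stands is narrower: change is the only contrast stated and powered, and baseline handling is not written down.

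**Nothing is biased.** A reader might also infer that the planned analysis is wrong. It is not: the change score is unbiased under randomization, and the plan's power figure reproduces.

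**A bigger modelling change is not free.** It is tempting to require a random intercept for the six Tele-Savvy groups in the same edit and call the whole a free gain. That fails. With no true clustering and ρ=0.5, adding that term lowers the adjusted model's simulated power from 89.3% to 81.5%. At ρ of 0.7, 0.8 and 0.9 it gives 74.9, 74.2 and 70.6%, below the plan's 79.7%. The opposite step, ignoring the groups, is also unsafe: with site and wave only, simulated type I error at ρ=0.5 was 6.9% at ICC 0.05. This is a separate question about clustering.

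**Attrition.** Comparing with a completers-only change score would overstate the gain. At 20% attrition it puts the plan at 70.2%, against 73.3, 72.4 and 71.5% for the all-data model at ρ of 0.3, 0.5 and 0.7.

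**It is a pilot.** Section 1 gives its three objectives equal importance, and section 9.1 makes enrolment the primary goal and sets the numbers by what one year allows. Precision on mastery is therefore useful but not decisive. That limits the weight of the point without removing it.

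**Conclusion.** The point holds as a matter of efficiency and pre-specification. Stating a common baseline mean or a baseline covariate gives a valid and more precise estimate of the same 3-month effect. Without attrition or clustering, the 95% interval narrows by 19% at ρ=0.3, 13% at 0.5 and 3% at 0.9, and power rises by about 14, 10 and 2 points. With attrition both analyses have less power and the gain is somewhat smaller. If group clustering is modelled in both analyses, power is also lower in both, but most of the relative gain in interval width remains.

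The size rests on assumed values of ρ, attrition and ICC, and on equal SDs at the two times. The direction does not depend on ρ, but the gain is small if ρ is 0.8 or more. It is a recommended improvement, not a correction of an error.

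**What to change.** In section 9.5, state that the primary estimate is the Tele-Savvy minus control difference in mastery at 3 months. It should come from the mixed model with one common baseline mean for both arms, or with baseline mastery as a covariate. State also that site and wave are fixed effects, kept whatever their p-values, because the randomization strings are made by site and wave. Keep the existing evaluation of cohort and site clustering. Decide separately whether a random intercept for the Tele-Savvy groups is mandatory, with its power cost in view.

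The cost is SAP wording. Every variable is already collected. Adjustment should lose no caregiver, since completed baseline forms precede randomization. Baseline as a covariate uses one degree of freedom, and site and wave use three.

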9 STATISTICAL CONSIDERATIONS

9.1 General Design Issues

Statistical hypothesis: Caregivers who participate in the Tele-Savvy intervention will experience greater improvement in *caregiver mastery* between baseline and 3 month follow-up compared to caregivers who receive the self-guided, online Caregiving During Crisis program.

Secondary hypotheses: Caregivers who participate in the Tele-Savvy intervention will experience greater improvement in *reactions to behavioral and psychological symptoms of ADRD and in caregiver stress* between baseline and 3 month follow-up compared to caregivers who receive the self-guided, online Caregiving During Crisis program.

In this pilot pragmatic clinical trial, our primary goal is to successfully enroll caregivers invited to participate in this study by clinical sites in health care systems within the daily workflow of clinical activities. Within the one-year time frame allowed for this pilot study, we determined that we could enroll, at each of the two clinical sites, 3 sequential Tele-Savvy programs. We further determined that we could introduce an attention control condition and randomly assign caregivers to receive Tele-Savvy or the control condition in waves, each wave representing a

caregivers participating in a distinct Tele-Savvy program and a comparison group of caregivers receiving the Caregiving During Crisis program.

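### Does section 9.5 leave open which test decides the between-arm mastery hypothesis?

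*Combined protocol and SAP*

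**What the plan says.** Section 9.1 hypothesises that Tele-Savvy caregivers "will experience greater improvement in *caregiver mastery* between baseline and 3 month follow-up compared to caregivers who receive the self-guided" control course.

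The power text in 9.5 takes 60 and 40 caregivers, counts baseline and 3 months as the two primary time points, and gives sizes detectable by repeated-measures ANOVA with 80% power at the 5% level. These are f=0.285 for group and, for the other two effects, "within subject time effect ($f=0.282$) and group-by-time treatment effect ($f=0.282". It adds: "This expected effect size is supported by previously measured improvements in caregiver mastery" in the earlier Tele-Savvy trial.

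Six months is an additional assessment of sustainability in about two thirds of caregivers (40 and 26). Section 9.4.1 schedules it at "6 months post-randomization for caregivers in the first and second waves". For that smaller sample 9.5 gives f=0.350 for group and f=0.388 for time and group-by-time. It then reports that "an effect size of $f=0.46$ was recorded for caregiver mastery improvements in active Tele-Savvy program participants".

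The analysis itself is by multilevel mixed models, to "utilize all data collected at each time point for all caregivers to assess changes in measures over time". Post hoc, "Post hoc pairwise comparisons between time points within subjects will be performed using Sidak error rate adjustments". An intention-to-treat analysis comes first, followed by a comparison of adherent with non-adherent caregivers. Tests are at 5%, and 95% intervals are promised for all effect sizes.

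**The concern.** The power text is written for a two-time-point ANOVA, but the analysis is a mixed model on up to three time points. The sentence that introduces the model speaks of change over time and mentions no arm. Once 6-month data are in the model, group-by-time could mean the 3-month contrast, a joint test of the 3- and 6-month differences, or a difference in slopes. The plan's own f=0.388 fits the joint test, which is not the contrast in 9.1.

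The within-subject comparisons raise a further worry. A gain within Tele-Savvy cannot be separated from the passage of time or from the control course. With 60 against 40 caregivers, the larger arm also reaches significance more easily when true gains are identical.

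The prior f=0.46 is described for Tele-Savvy participants, with no control figure, time points or SD. It does not by itself support a between-arm effect of f=0.282. If the deciding test could be chosen after seeing the data, or a within-arm gain presented as effectiveness, the trial's main claim would be unreliable.

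**Working it through.** **1. The plan's power figures** (noncentral F, noncentrality λ = N·f²)

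| N | f | λ | df | Power |
|---|---|---|---|---|
| 100 | 0.282 (time, group-by-time) | 7.95 | 1, 98 | 79.7% |
| 100 | 0.285 (group) | 8.12 | 1, 98 | 80.6% |
| 66 | 0.350 (group) | 8.09 | 1, 64 | 80.0% |
| 66 | 0.388 (group-by-time) | 9.94 | 2, 128 | 80.3% |
| 66 | 0.388, read as 1 df | 9.94 | 1, 64 | 87.4% |

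The figures reproduce. At 60:40, f=0.282 is a between-arm difference of 0.282/√(0.6×0.4) = 0.576 SD of change. The three-time-point figure was computed as a 2-df test, for N = 40+26 = 66.

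**2. Which contrast the text implies**

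| Element | Where it is fixed |
|---|---|
| Outcome: mastery | 9.1, 9.4.1 |
| Comparator: control course | 9.1 |
| Interval: baseline to 3 months | 9.1; primary time points in 9.5 |
| Effect: group-by-time, labelled the treatment effect | 9.5, power text |
| Population: intention to treat | 9.5 |
| Role of 6 months: sustainability | 9.5 |
| Model term and coding of time | not written |

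With two time points, group-by-time is exactly the between-arm difference in change to 3 months. Only the last row is missing.

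**3. What a departure would cost.** Assumptions: 60/40 at baseline and 3 months, 40/26 at 6 months, compound symmetry, correlation 0.5, a difference of 0.578 SD of change (80% power at 60:40), no clustering or dropout. Generalised least squares gives:

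| True difference | 3-month contrast | 2-df test | Linear slope |
|---|---|---|---|
| Sustained at 6 months | 80% | 80% | 77% |
| Halved at 6 months | 80% | 71% | 36% |
| Gone at 6 months | 80% | 80% | 8% |
| Only at 6 months | 5% | 67% | 60% |

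Correlations of 0.3 and 0.7 move these by no more than about 0.014. In simulation (20,000 draws), the 3-month and 2-df tests disagree in 17% of trials at a sustained 0.4 SD and 11% at 0.58 SD. The plan mentions no slope test.

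**4. Within-arm reading.** Assume equal true gains in both arms and one-sample t tests at the Sidak level for three pairs, 1 − 0.95^(1/3) = 0.017. The last column is (Tele-Savvy) × (1 − control).

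| Gain (SD of change) | Tele-Savvy significant | Control significant | Tele-Savvy only |
|---|---|---|---|
| 0.2 | 19% | 12% | 17% |
| 0.3 | 45% | 29% | 32% |
| 0.4 | 74% | 52% | 35% |
| 0.46 | 86% | 66% | 29% |

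A two-sided 5% between-arm test would favour Tele-Savvy in 2.5%. These rates apply only if the comparisons are run by arm, set against each other and used to conclude effectiveness. Section 9.5 says none of these things.

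**5. The prior f=0.46.** Its scale is not given, so two readings are assumed, with between-arm f = difference × √0.24.
- Tele-Savvy change of 0.46 SD: f=0.225 and power 61% if control does not change; f=0.113 and 20% if control gains half as much.
- Tele-Savvy change of 0.92 SD: f=0.451 and 99%; f=0.225 and 61%.

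This range bears on how likely an effect of f=0.282 is. It does not alter the detectable effects in step 1.

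**The case for a change.** The strongest case for a change is that inferring group-by-time does not fix the test. The mixed model will use all three time points, f=0.388 shows that a 2-df interaction was in mind for three of them, and step 3 shows that the choice can alter the answer. Section 1.1 commits to testing the mastery hypothesis and 9.5 claims 80% power, so pilot status is no excuse. One paragraph would settle it at no cost in participants or data.

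Part of this stands: the model sentence does not restate the arm-by-time term or say how time is coded, and f=0.46 is undefined.

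The rest is weaker. The f=0.388 is the power statement for the smaller sample with 6-month data, which 9.5 keeps apart from the primary time points, so it is a poor guide to the primary test. A within-arm change cannot answer 9.1, which requires a comparison with control. It would also go too far to say that 9.5 specifies only within-subject comparisons: it names group and group-by-time effects and an adherence comparison. The lowest power figures come from a slope test that appears nowhere in the plan. Among the three patterns with a true 3-month difference, the 2-df test loses power only when the difference is halved, by about 9 points.

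**Conclusion.** No change to the plan follows. This is a gap that an analyst fills sensibly: 9.1 and the power text in 9.5 together imply a mixed model with arm, time and their interaction, and a primary contrast for the between-arm difference in mastery change from baseline to 3 months. That test has about 80% power for 0.58 SD of change, as the plan states, before clustering and dropout. Writing it out would record what is already implied.

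The 17% to 35% and the slope figures are illustrations of analyses that the plan does not make decisive; they are not error rates of this trial. The undefined f=0.46 limits how far the prior trial supports the expected effect. Section 9.1 bases the number of programmes on what could be enrolled in one year, so a different reading of f=0.46 would change neither the sample nor the analysis. The conclusion assumes that the analyst reads 9.5 with 9.1. A report that rested effectiveness on a within-arm gain would depart from the stated hypothesis.

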Tele-Savvy is a psychoeducation program designed to build not only knowledge and skill but also confidence. The psychoeducation approach uses three main strategies to accomplish this goal. The first strategy is instruction, providing information that helps caregivers increase their fund of knowledge for caregiving. The second strategy involves active learning, accomplished by interactive exercises conducted during the course; for example, thinking about how, given what the caregiver now understands about the cognitive losses in dementia, to best convey information to the person living with dementia. Active learning is also accomplished by asking course participants to try these strategies during the regular course of home caregiving -- this is what we refer to as "homework" -- the real life application of what is taught in class in the home setting. The third approach involves acknowledging caregiving success through a process of reporting back on caregiving activities during the week, particularly those that involved trying out the caregiving strategies taught in class. Reporting success and observing the caregiving successes of other participants is an important means of building and reinforcing caregiver confidence and competence.

The attention control group will receive the self-guided Caregiving During Crisis program. Caregiving During Crisis is a fully online, asynchronous, professionally designed continuing education course aimed at developing the competency of informal caregivers of community-dwelling persons living with dementia to ensure the safety of that person and themselves during this time of the COVID-19 pandemic. The course, readily accessible by home computer or smartphone, describes methods of home infection control and prevention to create a Safe Home space, strategies for safely leaving and re-entering the home (e.g., to shop), additional strategies for safely allowing service personnel (e.g., home health aides or electricians) and select family members to enter the Safe Home space, and risk management strategies to frame decisions when/if COVID restrictions are relaxed or revoked.

Two-thirds of the 100 caregivers (the first 67 caregivers) enrolled in the study will be on study for 6 months, and one-third of the caregivers (the final 33 caregivers) will be on study for 3 months.

Sample Size and Population

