5 STUDY INTERVENTIONS

5.1 Interventions, Administration, and Duration

The Tele-Savvy program, *a low-risk, psychoeducational, group-based intervention*, is grounded in social learning and stress process theory and its main goal is to produce improved caregiver mastery over the symptom management skills commonly encountered when supervising and caring at home for an older adult living with ADRD. Over the 7-week program, there are synchronous and asynchronous activities each week. The synchronous portion includes weekly scheduled videoconferences (60-80 min) that serve as an online classroom in which facilitators lead lectures and discussions and provide a venue for caregivers' interactions and sharing of their experiences. The majority of Tele-Savvy is asynchronous. Daily, caregivers access online 6- to 15-min prerecorded videos, each focused on one main learning objective. The lessons' didactic messages are delivered through expert presentations that are usually augmented by vignettes enacted by amateur actors playing a "caregiving family" in various dementia-stage-specific caregiving situations and using caregiving strategies in familiar settings. Caregivers can watch the lessons whenever and as often as they wish. The Canvas platform at Emory University houses the Tele-Savvy software that includes analytics to monitor caregivers' use of asynchronous material each week. Topics of the synchronous sessions progress from cognitive losses through caregivers' emotions, guiding behavior and decision-making skills, and family systems. Videos depicting caregiving situations follow a similar course as the more didactic videoconference topic presentations each week, ending with increasing caregiver mastery and the concept of caregiver village.

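### Section 9.5 leaves clustering by Tele-Savvy group to an undefined check of cohort number, and its 80% power holds only if caregivers are independent

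*Combined protocol and SAP*

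**What the plan says.** Assignment is by individual caregiver: section 9.2.1 says "caregivers will be randomly assigned at a 3:2 ratio to either Tele-Savvy or the attention control group", and section 6.2.2 applies the randomization string as each caregiver returns the baseline forms. The Tele-Savvy arm is then assembled into groups, "for a total of 60 caregivers in 6 Tele-Savvy cohorts". Section 5.1 describes weekly videoconferences "that serve as an online classroom in which facilitators lead lectures and discussions and provide a venue for" interaction among caregivers, though it adds "The majority of Tele-Savvy is asynchronous". The précis makes the group part of the mechanism: "Reporting success and observing the caregiving successes of other participants is an important means of building and reinforcing caregiver confidence and competence". Controls use a self-guided course individually (section 5.2).

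On the analysis, section 9.5 says "MLM will also adjust for the non-independence of the data collected across time nested within each subject". Grouping gets one further sentence: "Cohort number and clinical site will also be evaluated to see if any additional clustering effects are noted within each cohort", or at each site. On power it says "This design is adequately powered at 80% power and 5% level of significance to detect medium effect sizes for the group effect" (f=0.285), and likewise for the group-by-time effect (f=0.282), with 60 and 40 caregivers and repeated measures ANOVA. There, group means treatment arm. No ICC, design effect or number of treatment groups enters the calculation.

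The documents use the word cohort in two ways. Section 9.2.1 uses it for the Tele-Savvy programmes. The précis (Sample Size and Population) also puts controls in three sequential cohorts of 6 to 7 per site. Section 4.3 generates randomization strings by site and wave, and section 9.1 defines a wave as a Tele-Savvy programme together with its comparison group.

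**The concern.** This is a partially nested design: individuals are randomized, one arm is then treated in groups, and the other is not. Mastery is scored on a four-item scale of self-perceived competence, and the précis says that peer exchange builds competence. Some correlation within Tele-Savvy groups is therefore plausible, although it may be small because most of the programme is done alone.

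If it exists, the Tele-Savvy mean is less precise than 60 independent caregivers would give. The level of the mastery test then depends on what happens to the cohort term, which 9.5 leaves open until the data are seen by a study team that section 5.2 describes as unmasked. With six groups, a check that finds nothing is weak evidence that nothing is there. The power statement is also more favourable than an analysis that respects the groups can deliver.

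**Working it through.** **Inputs from the documents.** 60 Tele-Savvy caregivers in 6 groups of 10 (three per site) and 40 controls (20 per site); two-sided 5%; f=0.282 for group-by-time; baseline and 3 months (sections 9.2.1 and 9.5).

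**Assumptions.** Complete change scores, total variance 1 in both arms, ICC of change 0 / 0.02 / 0.05 / 0.10.

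**Step 1: the plan's own figure.** With independent caregivers the noncentrality is N·f² = 100 × 0.282² = 7.95. On 1 and 98 df this gives 79.7% power; f=0.285 gives 80.6%. The 6-month figures reproduce in the same way with N=66: f=0.350 gives 80.0% (1, 64 df) and f=0.388 gives 80.3% (2, 128 df). No allowance for clustering is hidden in them.

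**Step 2: clustering alone.** The standardized difference is d = 0.282/√(0.6×0.4) = 0.576. The standard error is √{[1+(10−1)·ICC]/60 + 1/40}. At ICC 0 it is 0.204 and d/SE = 2.82, so normal-approximation power is Φ(2.82−1.96) = 80.5%. At ICC 0.05 the design effect is 1.45, SE = 0.222 and d/SE = 2.60, giving 74%. ICC 0.02 and 0.10 give 78% and 68%.

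**Step 3: variance specific to Tele-Savvy groups (simulation).** The check is a one-way F test across the six groups (5, 54 df). If the term is kept, a group-level Welch/Satterthwaite test follows; otherwise a pooled t-test. The last two rows always model the group with site fixed (4 df between groups, 38 df for controls).

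| Assumed group ICC | 0 | 0.02 | 0.05 | 0.10 |
|---|---|---|---|---|
| 5% check finds clustering | 5% | 10% | 19% | 35% |
| Type I error, kept if significant at 5% | 4.8% | 5.3% | 5.9% | 6.7% |
| Type I error, kept if significant at 20% | 4.3% | 4.6% | 5.0% | 5.4% |
| Type I error, kept if estimate positive | 3.9% | 4.1% | 4.5% | 4.9% |
| Type I error, term left out | 5.0% | 5.7% | 7.0% | 9.3% |
| Type I error, always modelled | 5.0% | 5.0% | 5.1% | 5.3% |
| Power at f=0.282, always modelled | 76% | 72% | 67% | 60% |

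The fall from 79.7% to 76% at ICC 0, about 4 points, is the degrees-of-freedom cost of having few groups. It is not an error in the plan's calculation.

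**Step 4: variance shared by both arms within a site-wave.** Give the 10 Tele-Savvy caregivers and 6 to 7 controls of each site-wave a common effect with variance 0.02 / 0.05 / 0.10, and no group effect. Ignoring it gives type I error of about 4.9 / 4.6 / 4.1%, with power about 80 to 81%. The always-modelled test of step 3, which treats controls as independent, becomes conservative: about 4.3 / 3.4 / 2.3%, with power down to 69% at 0.05 and 62% at 0.10. With 0.05 split equally between wave and group, ignoring both gives 5.8%; the step 3 test gives 4.2% and 68% power.

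The size and direction of the problem therefore depend on which kind of cohort carries the variance, and 9.5 does not separate the two.

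**The case against.** The strongest reply has four parts.

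- **Section 9.5 does not ignore clustering.** It names cohort and site for evaluation. A reader might infer from the bottom of the range that the trial runs at 7 to 9% type I error. The documents do not support that. It requires an ICC of 0.05 to 0.10, all of it specific to Tele-Savvy groups, and a check that ends with the term left out. Under looser retention rules the error stays near or below 5%.
- **The variance may be a wave effect.** Recruitment runs in site-waves shared by both arms, and a shared effect largely cancels in the comparison. This stands, and it also means that a group term added with no wave term could cost power where no inflation exists.
- **Part of the power loss comes from the stricter analysis.** This stands too: about 4 points arise at ICC 0. A reader might call the 80% a miscalculation. It is not; it is correct for independent caregivers.
- **This is a pilot.** Section 9.1 makes enrolment the primary goal and takes the number of programmes from the one-year time frame, so restated power would not change the size. Section 9.5 also cites f=0.46 from the earlier trial, at which power would be about 96% at ICC 0.10. The text ties that value to active Tele-Savvy participants, however, so it is not established as a between-arm effect, and it would not protect the type I error.

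What remains is that 9.5 gives no rule, does not say which grouping it means, and states power without the independence assumption.

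**Conclusion.** The concern holds in a limited form. Section 9.5 leaves the handling of grouping open until the data are seen, and the check it describes has little power with six groups. For variance specific to the Tele-Savvy groups, the likely type I cost is about 1 to 2 points at an ICC of 0.05 to 0.10 if the term is kept only when significant. It is little or none under looser rules, or if the variance is shared by wave. The power statement is affected more: with the group always modelled, 80% becomes about 76 / 72 / 67 / 60% at ICC 0 / 0.02 / 0.05 / 0.10, with no wave variance. Every ICC here is assumed, and dropout is not modelled.

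The précis calls the trial cluster randomized. A reader might infer that whole groups are allocated, but sections 6.2.2 and 9.2.1 assign individuals. That label is a separate inconsistency and changes none of these figures.

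This is worth correcting because the trial still states an effectiveness hypothesis, 5% tests and 80% power, but its weight in a pilot is modest.

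**What to change.** In section 9.5:

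1. Define cohort number, distinguishing the site-by-wave recruitment stratum shared by both arms from the Tele-Savvy treatment group.
2. Prespecify a random effect for the six Tele-Savvy groups, in that arm only and kept regardless of significance, with site fixed and Satterthwaite or Kenward-Roger degrees of freedom. State how the shared wave enters, for example as a random site-by-wave term common to both arms, so that wave variance is not charged to the treatment contrast. Arm-specific residual variances are optional.
3. Report the group ICC with its confidence interval. Six groups will estimate it imprecisely, but it would inform a later trial.
4. State that the 80% assumes independence, and give power at f=0.282 over an assumed ICC range. The 76 / 72 / 67 / 60% above are for the site-fixed group-level test without wave variance and should be recomputed for the final model. Note that about 4 points of the loss come from the small number of groups.

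Separately, reconcile the cluster-randomized label in the précis with the individual assignment in sections 6.2.2 and 9.2.1.

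The cost is wording only, with no change to sample size or conduct. The downside is a less favourable stated power and wider intervals. For the site-fixed group-level test, the mean 95% half-width is about 0.42 / 0.44 / 0.47 / 0.51 SD at ICC 0 / 0.02 / 0.05 / 0.10, against 0.40 SD with cohort ignored.
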